9.4 STATISTICAL ANALYSIS

9.4.1 General Approach

Various pharmacokinetic parameters will be calculated, including area under the time curve (0-t and 0-infinity), clearance, volume of distribution at steady-state, T_{max} and C_{max} , and terminal (beta phase) $t_{1/2}$, will be calculated. A semi-parametric model described by Lee et al⁴⁰ will be used to calculate the terminal $t_{1/2}$. Other parameters will be calculated using a standard noncompartmental approach. Descriptive statistics will be reported for each parameter and will include mean \pm standard deviation and median \pm interquartile range.

The evaluation of the primary endpoint is descriptive, but 95% confidence intervals will be calculated as appropriate.

There will be a formal Statistical Analysis Plan (SAP) completed prior to database lock.

Dalcinonacog alfa_DLZ-201 VERSION 2.0, Amendment 1

9.4.2 Analysis of the Primary Efficacy Endpoint(s)

The analysis of the primary endpoint will include:

- Number of subjects who achieve a steady-state FIX activity level above 12% with daily dosing.

9.4.3 Analysis of the Secondary Endpoint(s)

Study drug exposure and compliance will be provided.

The following parameters will be documented:

- Occurrence of clinical thrombotic event not attributable to another cause, and occurrence of antibody formation resulting in a decreased endogenous level of FIX.
- Change in coagulation parameters (fibrinogen, and FIX activity levels) from pre-dose.
- Occurrence of an antibody response to CB2679d and whether it is inhibitory and cross-reactive to BeneFIX®.
- Clinically significant levels of thrombogenicity markers resulting from SC administration of CB2679d

The frequencies of these events will be summarized as proportions and counts.

Protocol deviations will be listed. All major protocol deviations (in particular those regarding entry criteria) will be summarized in the study report.

9.4.4 Safety Analysis

Adverse Events

All AEs will be listed, documenting the course, outcome, severity, and causality to study drug. Verbatim terms on CRFs will be mapped to preferred terms and related system organ class using the Medical Dictionary for Regulatory Activities (MedDRA).

Incidence rates of AEs and the proportion of subjects prematurely withdrawn from the study due to AEs will be shown for. Incidence rates will also be displayed based on severity and relationship to study drug. AEs with a relationship of "possibly" or "probably" related will be considered by the Sponsor as "related" to the study drug. Events assessed as "unrelated", "unlikely" related, or where the

Dalcinonacog alfa_DLZ-201 VERSION 2.0, Amendment 1

relationship was not reported will be considered by the Sponsor as "not related" to the study drug. The incidence of SAEs will be provided. All incidence rates will be categorized and displayed by system organ class and preferred term.

Vital Signs

Safety analyses will include descriptive statistical summaries of shifts in vital signs (blood pressure, heart rate, respiratory rate) and in laboratory values.

9.4.5 Baseline Descriptive Statistics

Demographic and baseline measurement variables will be summarized using descriptive statistics.

9.4.6 Planned Interim Analyses

Not applicable to this study.

9.4.7 Sub-Group Analyses

Not applicable to this study.

9.4.8 Tabulation of Individual Participant Data

Individual participant data will be listed by measure and time point.

Dalcinonacog alfa_DLZ-201 VERSION 2.0, Amendment 1

10. SUPPORTING DOCUMENTATION AND OPERATIONAL CONSIDERATIONS

10.1 REGULATORY, ETHICAL AND STUDY OVERSIGHT CONSIDERATIONS

10.1.1 Informed Consent Process

The written informed consent documents will be prepared in the language(s) of the potential subject population, based on an English version provided by the Sponsor and should be easy to understand.

Before a subject's participation in the trial, the investigator is responsible for obtaining written information consent from the subject after adequate explanation of the aims, methods, anticipated benefits, and potential hazards of the study and before any protocol specific screening procedures or any study drugs are administered. Sufficient time must be given to consider whether to participate in the study.

The informed consent form should be signed and personally dated by the subject and by the study person who conducted the informed consent discussion. The original signed informed consent form should be retained in the Study Master File and in any other locations required by institutional policy, and a copy of the signed consent form should be provided to the subject.

10.1.2 Institutional Review Board/Independent Ethics Committee

Before initiation of the study, the investigator must submit for approval the protocol, ICF, Investigator's Brochure, and any advertisements to an IRB/IEC for written approval. The Investigator must ensure IRB/IEC compliance with the applicable regulations. A copy of written IRB/IEC approval of the protocol, ICF, and all advertisements must be provided to Sponsor or designee prior to initiation of the study and shipment of study drug. The Investigator is responsible for obtaining continued review of the clinical research at intervals not exceeding one year or at more frequent intervals if specified by the IRB/IEC. The Investigator must supply Sponsor or designee with written documentation of continued review of the clinical research.

The Investigator is responsible for reporting the following to the IRB/IEC:

- All SAEs (including deaths) regardless of cause and whether anticipated or unanticipated (reported immediately)
- Significant findings that become known in the course of the study that might affect the willingness of subjects to continue to participate

Dalcinonacog alfa_DLZ-201 VERSION 2.0, Amendment 1

- Protocol, or consent amendments prior to the implementation of the change
- Study progress reports at least once a year, if applicable
- Notification of study completion or termination.

Sponsor may amend the protocol as needed to ensure that the clinical investigation is being conducted as intended. Sponsor will initiate protocol amendments in writing if any change significantly affects the safety of subjects, the scope of the investigation, or the scientific quality of the study. Protocol changes must be submitted to the IRB/IEC as a protocol amendment. If necessary, the ICF will be revised to reflect the changes in the amendment and will be submitted to the IRB/IEC for review and approval. A copy of the amendment must be signed by the Investigator and returned to Sponsor or designee. Written documentation of IRB/IEC approval is required before the amendment is implemented. Investigators may not perform study-specific assessments that are not included in the protocol unless agreed to by Sponsor.

10.1.3 Study Discontinuation and Closure

This study may be temporarily suspended or prematurely terminated if there is sufficient reasonable cause. Written notification, documenting the reason for study suspension or termination, will be provided by the suspending or terminating party to study subjects, investigator, and regulatory authorities. If the study is prematurely terminated or suspended, the PI will promptly inform study participants, the IRB/IEC, and sponsor and will provide the reason(s) for the termination or suspension. Study subjects will be contacted, as applicable, and be informed of changes to study visit schedule.

When a study is prematurely terminated, refer to **Section 7, Study Intervention Discontinuation and Participant Discontinuation/Withdrawal**, for handling of enrolled study participants.

10.1.4 Confidentiality and Privacy

Participant confidentiality and privacy is strictly held in trust by the participating investigators, their staff, and the sponsor, or designee. The study protocol, documentation, data, and all other information generated will be held in strict confidence. No information concerning the study, or the data will be released to any unauthorized third party without prior written approval of the sponsor.

All research activities will be conducted in as private a setting as possible.

Dalcinonacog alfa_DLZ-201 VERSION 2.0, Amendment 1

The study monitor, other authorized representatives of the sponsor, representatives of the IRB/IEC, or regulatory agencies may inspect all documents and records required to be maintained by the investigator, including but not limited to, medical records (office, clinic, or hospital) and pharmacy records for the participants in this study. The clinical study site will permit access to such records.

The study participant's contact information will be securely stored at each clinical site for internal use during the study. At the end of the study, all records will continue to be kept in a secure location for as long a period as dictated by the reviewing IRB/IEC, Institutional policies, or sponsor requirements.

10.1.5 Future Use of Stored Specimens and Data

There is no genetic testing performed in relation to this study.

10.1.6 Clinical Monitoring

Clinical site monitoring is conducted to ensure that the rights and well-being of trial participants are protected, that the reported trial data are accurate, complete, and verifiable, and that the conduct of the trial is in compliance with the currently approved protocol/amendment(s), with ICH GCP, and with applicable regulatory requirement(s).

The Sponsor, or its designee, and regulatory authority inspectors are responsible for contacting and visiting the Investigator for the purpose of inspecting the facilities and, upon request, inspecting the various records of the trial (e.g., CRFs and other pertinent data) provided that subject confidentiality is respected. The Sponsor monitor is responsible for inspecting the CRFs at regular intervals throughout the study to verify adherence to the protocol; completeness, accuracy, and consistency of the data; and adherence to local regulations on the conduct of clinical research. The monitor should have access to subject medical records and other study-related records needed to verify the entries on the CRFs. The Investigator agrees to cooperate with the monitor to ensure that any problems detected in the course of these monitoring visits, including delays in completing CRFs, are resolved.

To ensure the quality of clinical data a clinical data management review will be performed on subject data received by the Sponsor. During this review, subject data will be checked for consistency, omissions, and any apparent discrepancies. In addition, the data will be reviewed for adherence to the protocol and GCP.

Dalcinonacog alfa_DLZ-201 VERSION 2.0, Amendment 1

Independent audits may be conducted by the Sponsor, or designee, or regulatory authority inspectors to inspect the Study Center facilities (e.g., pharmacy, drug storage areas, laboratories) and review of study related records to evaluate the trial conduct and compliance with the protocol, ICH GCP, and applicable regulatory requirements.

The Principal Investigator will sign and date the indicated places on the CRF. These signatures will indicate that the principal Investigator inspected or reviewed the data on the CRF, the data queries, and the Study Center notifications, and agrees with the content.

10.1.7 Quality Assurance (QA) and Quality Control (QC)

The Sponsor, or designee, will be responsible for data management of this study, including quality checking of the data. Sites will be responsible for data entry into the electronic data capture (EDC) system (eCRFs). In the event of data discrepancy, the Sponsor, or designee, will request data clarification from the sites, which the sites will resolve electronically in the EDC system.

The eCRFs and correction documentation will be maintained in the EDC system audit trail.

Diary data will be entered into the eCRF.

Following written Standard Operating Procedures (SOPs), the monitors will verify that the clinical trial is conducted, and data are generated, and biological specimens are collected, documented (recorded), and reported in compliance with the protocol, ICH GCP, and applicable regulatory requirements (e.g., Good Laboratory Practices [GLP], GMP).

The investigational site will provide direct access to all trial related sites, source data/documents, and reports for the purpose of monitoring and auditing by the sponsor, and inspection by local and regulatory authorities.

10.1.8 Data Handling and Record Keeping

10.1.8.1 Data Collection and Management Responsibilities

Data collection is the responsibility of the clinical trial staff at the site under the supervision of the site investigator. The investigator is responsible for ensuring the accuracy, completeness, legibility, and timeliness of the data reported.

Dalcinonacog alfa_DLZ-201 VERSION 2.0, Amendment 1

All source documents should be completed in a neat, legible manner to ensure accurate interpretation of data.

Clinical data (including AEs, concomitant medications, and expected adverse reactions data) and clinical laboratory data will be entered into Medidata Rave EDC, a 21 CFR Part 11-compliant data capture system. The data system includes password protection and internal quality checks, such as automatic range checks, to identify data that appear inconsistent, incomplete, or inaccurate. Clinical data will be entered directly from the source documents.]

10.1.8.2 Study Records Retention

Study documents should be retained as required by local regulations. No records will be destroyed without the written consent of the sponsor, if applicable. It is the responsibility of the sponsor to inform the investigator when these documents no longer need to be retained

10.1.9 Protocol Amendments

Sponsor may amend the protocol as needed to ensure that the clinical investigation is being conducted as intended. Sponsor will initiate protocol amendments in writing if any change significantly affects the safety of subjects, the scope of the investigation, or the scientific quality of the study. Protocol changes must be submitted to the IRB/IEC as a protocol amendment. If necessary, the ICF and assent form will be revised to reflect the changes in the amendment and will be submitted to the IRB/IEC for review and approval. A copy of the amendment must be signed by the Investigator and returned to Sponsor or designee. Written documentation of IRB/IEC approval is required before the amendment is implemented. Investigators may not perform study-specific assessments that are not included in the protocol unless agreed to by Sponsor. Additionally, a site-specific amendment and revised ICF and assent form must be generated and submitted for approval to the IRB/IEC.

10.1.10 Publication and Data Sharing Policy

The final clinical study report is also intended to form the basis for a manuscript intended for publication in a peer-reviewed scientific journal. The authorship, timetable and any arrangements for review by the participating investigators will be coordinated by Catalyst Biosciences. No partial subset of data from

Dalcinonacog alfa_DLZ-201 VERSION 2.0, Amendment 1

individual investigational sites can be presented or published until after the primary manuscript for the entire study has been accepted for publication in a peer reviewed scientific journal.

10.2 PROTOCOL AMENDMENT HISTORY

Version	Date	Description of Change	Brief Rationale
1.0	23 March 2018		
2.0, Amendment 1	17 October 2018	Removed Part 2 and 3	

Dalcinonacog alfa_DLZ-201 VERSION 2.0, Amendment 1

APPENDIX A – CLINICAL SIGNS OF THROMBOSIS

 American Heart Association.
life is why™

LOCAL INFO | LF

[f](#) [Twitter](#) [YouTube](#) [G+](#)

HEALTHY LIVING | **CONDITIONS** | SUPPORT | PROFESSIONAL | RESEARCH | EDUCATOR | CPR & ECC

Arrhythmia Cholesterol Congenital Defects Children & Adults Heart Attack Heart Failure High Blood Pressure

Symptoms and Diagnosis of Venous Thromboembolism (VTE)

[in Share](#)

0

[Like](#) 2

[Tweet](#)

[G+1](#)

2

[Share](#)

48

Updated:Mar 9,2017

VTE includes deep vein thrombosis (DVT), when a blood clot forms in a deep vein, usually in the leg. And it includes pulmonary embolism (PE), when the clot breaks off and travels from the leg up to the lungs. DVT and PE are serious, life-threatening conditions that require immediate medical attention.

What are the warning signs?

DVT mainly affects the large veins in the lower leg and thigh, almost always on one side of the body at a time. The clot can block blood flow and cause:

- Leg pain or tenderness of the thigh or calf
- Leg swelling (edema)
- Skin that feels warm to the touch
- Reddish discoloration or red streaks

PE, or pulmonary embolism, can be fatal and occurs when the DVT breaks free from a vein wall and blocks some or all of the blood supply to the lungs, causing:

[figure not shown]
- Unexplained shortness of breath
- Rapid breathing
- Chest pain anywhere under the rib cage (may be worse with deep breathing)
- Fast heart rate
- Light headedness or passing out

http://www.heart.org/HEARTORG/Conditions/VascularHealth/VenousThromboembolism/Symptoms-and-Diagnosis-of-Venous-Thromboembolism-VTE_UCM_479057_Article.jsp#

Dalcinonacog alfa_DLZ-201 VERSION 2.0, Amendment 1

Common Heart Attack Warning Signs

[figure not shown]

Learn more at Heart.org/HeartAttack.

©2016 American Heart Association, Inc. All rights reserved. Unauthorized use prohibited.

http://www.heart.org/HEARTORG/Conditions/HeartAttack/WarningSignsofHeartAttack/Warning-Signs-of-a-Heart-Attack_UCM_002039_Article.jsp#.WkkEAWeYpfw

Dalcinonacog alfa_DLZ-201 VERSION 2.0, Amendment 1

[figure not shown]

**Use the letters in "fast" to spot stroke signs and
know when to call 9-1-1.**

http://www.strokeassociation.org/STROKEORG/WarningSigns/Stroke-Warning-Signs-and-Symptoms_UCM_308528_SubHomePage.jsp

Dalcinonacog alfa_DLZ-201 VERSION 2.0, Amendment 1

ADDITIONAL SYMPTOMS OF STROKE

Sometimes other symptoms appear, separately, in combination or with F.A.S.T. signs.

- 01** Sudden confusion, trouble speaking or understanding speech.
- 02** Sudden numbness or weakness of face, arm or leg. Especially on one side of the body.
- 03** Sudden trouble seeing in one or Both eyes.
- 04** Sudden trouble walking, dizziness, loss of balance or coordination.
- 05** Sudden severe headache with no known cause.

If someone shows any of these symptoms, call 9-1-1 or emergency medical services immediately.

Dalcinonacog alfa_DLZ-201 VERSION 2.0, Amendment 1

Symptoms and Signs of Venous Thromboembolism – Deep Vein Thrombosis (DVT) and Pulmonary Embolism (PE):

Leg pain or tenderness of the thigh or calf

Leg swelling (edema)

Skin that feels warm to the touch

Reddish discoloration or red streaks

Unexplained shortness of breath

Rapid breathing

Chest pain anywhere under the rib cage (may be worse with deep breathing)

Fast heart rate

Light headedness or passing out

Common Heart Attack Warning Signs

Pain or discomfort in the chest

Lightheadedness, nausea, or vomiting

Jaw, neck, or back pain

Discomfort or pain in arm or shoulder

Shortness of breath

Stroke Signs

Face Drooping

Arm Weakness

Speech Difficulty

Sudden confusion, trouble speaking or understanding speech

Dalcinonacog alfa_DLZ-201 VERSION 2.0, Amendment 1

Sudden numbness or weakness of face, arm or leg. Especially on one side of the body.

Sudden trouble seeing in one or both eyes.

Sudden trouble walking, dizziness, loss of balance or coordination.

Sudden severe headache with no known cause.

Dalcinonacog alfa_DLZ-201 VERSION 2.0, Amendment 1

Signs and Symptoms of Thrombosis

The clinical spectrum of venous thromboembolism (VTE) ranges from deep vein thrombosis (DVT) to pulmonary embolism (PE). The symptoms of VTE depend on the location of the affected vessel and whether the vessel is totally or partially occluded by the clot.

Table. Clinical Spectrum of VTE

Type	Signs and Symptoms	Physical Examination
Deep vein thrombosis (DVT) 
Blood clots may form in the deep blood vessels, most commonly in the legs and groin, and can block normal blood flow returning from the legs to the heart.Venous clots that form in regions of slow to moderate flow are composed of a mixture of red cells, platelets, and fibrin and are known as mixed platelet fibrin thrombi.Partially occlusive venous thrombosis of the deep veins in the legs or abdomen may present with subtle symptoms and sometimes may not present until significant collateral circulation* has developed.	
PainSwelling of the affected extremity/area with erythema and warmth over the vicinity of the clotDiscoloration including a bluish or suffused color	
Positive Homan's sign: pain with dorsiflexion of the footSwellingPain on palpationPresence of a palpable cordEvidence of collateral circulation, usually manifested by increased prominence of superficial veinsSome people with a DVT may be asymptomatic

Dalcinonacog alfa_DLZ-201 VERSION 2.0, Amendment 1

Pulmonary Embolism (PE)
 
• PE results from a piece or all of a blood clot that breaks off and is carried by the blood stream to the lung where it obstructs the blood vessel.• The size of the clot and the site of the obstruction of blood flow in the vessel determine the extent and severity of the pulmonary embolus.• Proximal vein thrombosis is more likely to lead to fatal PE as compared to calf vein thrombosis.• The incidence of fatal PE can be markedly reduced if DVT is treated with anticoagulant therapy.	
Pulmonary emboli may present subtly with the following complaints listed in order of frequency:
 
• Dyspnea• Rapid breathing, fast heartbeat and chest pain especially with inhalation• Pleural pain: Some patients notice only a dull ache in their chest• Apprehension, anxiety• Cough• Hemoptysis• Sweats• Syncope• Fatigue	
• Tachypnea• Tachycardia• Rales• Fever• Sweating• Thrombophlebitis• Accentuation of the pulmonary closure sound• Gallop heart sound• Cyanosis• Some people with a PE may be asymptomatic

Superficial Thrombophlebitis
 
• Superficial thrombophlebitis is due to blood clots that form in veins that are closer to the surface of the skin and are associated with inflammation.	
• These clots often partially block blood flow in affected veins and may cause pain and irritation.• Redness and inflammation along the vein may occur; if hard and erythematous, the affected vein is often visible and most commonly occurs in the legs or arms.	

Dalcinonacog alfa_DLZ-201 VERSION 2.0, Amendment 1

• Superficial thrombophlebitis is often observed in individuals who are heterozygous or homozygous for the factor V Leiden mutation.	
• Other associated symptoms include warmth and tenderness, surrounding purities and swelling.• Pain along the vein: patients may report a throbbing or burning sensation beneath the skin's surface; these symptoms may interfere with sleep as they progress. 
Fever: Patients with venous inflammation may develop an elevated temperature associated with an episode of thrombophlebitis.

--	---

Adapted from IHTC. Signs and Symptoms of Thrombosis. Available at <http://www.ihtc.org/payors/conditions-we-treat/clotting-disorders/signs-and-symptoms-of-thrombosis>.

Dalcinonacog alfa_DLZ-201 VERSION 2.0, Amendment 1

APPENDIX B – DETAILED STUDY SCHEMA

SCREENING

Up to 4 weeks prior

Screening

- Obtain informed consent
- Review demographic parameters
- Conduct a joint evaluation as per the SOC at hemophilia treatment center
- Screen potential subjects by inclusion and exclusion criteria
- Obtain medical and hemophilia history, document
- Check vital signs, height and weight
- Conduct physical examination, check for clinical signs of thrombosis
- Conduct testing for hematology and chemistry, coagulation assay, thrombogenicity markers, immunogenicity assays, genotyping and ECG

Dalcinonacog alfa_DLZ-201 VERSION 2.0, Amendment 1

Treatment – 28 days	
Day 1 Pre-IV Dose – 5 min	Day 1

• Evaluate concomitant medications, check vital signs, and weight• Conduct physical examination, check for clinical signs of thrombosis• Conduct testing for hematology and chemistry, thrombogenicity markers, PK sampling• Conduct study subject diary training	
Day 1 IV Dose Followed by SC Dose; Day 2 to Day 28 SC Dose	Day 1

• Day 1: Administer single IV 70 IU/kg loading dose of Dalcenonacog alfa• Day 1: 30 minutes later administer SC 140 IU/kg dose of Dalcenonacog alfa• Day 2 to 28: Administer SC 140 IU/kg dose of Dalcenonacog alfa	
Post-Dose SC Dose – (30 min and Hr 7)	Day 1

• Evaluate concomitant medications and check vital signs• Conduct physical examination, check for clinical signs of thrombosis• Conduct testing for thrombogenicity markers, PK sampling• Diary entry of bleeding episodes, AEs, injection site assessment• Check for AEs• Conduct platelet count only on Day 1, Hour 7	
24 Hours Post-SC Dose	Day 2

• Evaluate concomitant medications and check vital signs• Conduct physical examination, check for clinical signs of thrombosis• Conduct testing for thrombogenicity markers, PK sampling• Diary entry of bleeding episodes, AEs, injection site assessment• Check for AEs	
Pre-SC Dose	Days 7, 14, 21, 28

• Evaluate concomitant medications and check vital signs• Conduct physical examination, check for clinical signs of thrombosis• Conduct testing for hematology and chemistry, thrombogenicity markers, PK sampling, immunogenicity assays• Diary entry of bleeding episodes, AEs, injection site assessment• Check for AEs	

Dalcinonacog alfa_DLZ-201 VERSION 2.0, Amendment 1

Washout Period - Days 29, 30, 31, 32, 33

- Evaluate concomitant medications, check for clinical signs of thrombosis
- Conduct testing for thrombogenicity markers, PK sampling
- Diary entry of bleeding episodes, AEs, injection site assessment, check for AEs

Unscheduled

- Review medical and hemophilia history, document
- Evaluate concomitant medications, check vital signs, and weight
- Conduct physical examination, check for clinical signs of thrombosis
- Conduct testing for hematology and chemistry, thrombogenicity markers, PK sampling, immunogenicity assays
- Diary entry of bleeding episodes, AEs, injection site assessment, check for AEs

End of study

- Evaluate concomitant medications and check vital signs and weight
- Conduct physical examination, check for clinical signs of thrombosis
- Conduct testing for hematology and chemistry, coagulation assay, thrombogenicity markers, PK sampling, immunogenicity assays
- Diary entry of bleeding episodes, AEs, injection site assessment, check for AEs

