1.3 SCHEDULE OF ACTIVITIES (SOA)

Study Period	Screening	Treatment Period								Wash-out ⁸	Unscheduled Visit	End of Study ⁹
Study Day	Day -28 to -1	Day 1, IV Pre-dose (-5 min)	Day 1, SC dose, 35 (±5) min Post IV	Day 2	Day 3	Day 7 (± 1 day)	Day 14 (± 1 day)	Day 21 (± 1 day)	Day 28 (± 1 day)	Days 29, 30, 31, 32, 33		
Informed Consent	X											
Demographic Parameters	X											
Inclusion and Exclusion Criteria	X											
Medical and Hemophilia History ²	X										X	
Vital Signs	X	X	X	X	X	X	X	X	X		X	X
Height (screening only) & Weight	X	X									X	X
Physical Examination ²	X	X	X	X	X	X	X	X	X		X	X
Clinical Signs of Thrombosis ³	X	X	X	X	X	X	X	X	X	X	X	X
Hematology and Chemistry ⁴	X	X		X		X	X	X	X		X	X
Coagulation Assays ⁵	X											X
Thrombogenicity Markers ⁵	X	X	X	X	X	X	X	X	X	X	X	X
Pharmacokinetic Sampling ⁵	X	X	X	X	X	X	X	X	X	X	X	X
Immunogenicity Assays ⁵	X					X	X	X	X		X	X
Genotyping	X											
ECG	X											
Diary entry training ⁶		X										
Diary entry of any bleeding episodes, AEs, injection site reactions ⁶						←	→					
Adverse Events	X			←	→							
Concomitant Medications	X			←	→							
CB2679d ⁷ Administration ⁸			X		←	→						

1. As per Standard of Care at hemophilia treatment center.
2. Complete evaluation at Screening followed by interim targeted evaluation, per Investigator's discretion, as indicated on presentation of subject at study visit. Joint evaluation will be performed at Screening.
3. **Clinical Signs of Thrombosis** per protocol
4. Local Laboratory: **Hematology** - CBC and platelet count. **Chemistry** - Sodium, potassium, chloride, bicarbonate, hepatic enzymes (ALT, AST, GGT), bilirubin, albumin, creatinine. For Days 2, 3, 7, 14, 21, and 28, blood will be collected at Pre-dose (- 5 minutes).
5. Central Laboratory: **Coagulation assays** - PT and aPTT. **Thrombogenicity markers** - Fibrinogen, D-dimer, F1+2, and TAT. **Pharmacokinetics** - FIX activity. **Immunogenicity assays** - to CB2679d and BeneFIX®. For Days 2, 3, 7, 14, 21, and 28, blood will be collected at Pre-dose (- 5 minutes).
6. Diary entry training and entry consists of investigational drug administration, injection site assessment, adverse events, any bleeding episodes & treatment.
7. IV load dose (50 IU/kg) followed by SC dose (100 IU/kg) 30 minutes (+ 30 mins) after. **Daily SC** (100 IU/kg) dosing until Day 28 (28 total SC doses).
8. Daily FIX activity levels needed unless FIX activity level known to be < 5%, as per local lab.

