3. OBJECTIVES

3.1 PRIMARY

The primary objective is:

- To evaluate the dose required to achieve steady-state FIX levels >12% of a SC prophylaxis treatment regimen of CB2679d, in adult subjects with hemophilia B.

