6.1.2 Dosing and Administration

This is an open-label study. Each subject will receive the study drug:

CB2679d loading dose of 50 IU/kg IV, followed 35 ± 5 minutes later with a 100 IU/kg, with SC administration daily until Day 28 (total 1 IV dose and 28 SC doses).

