3.7. Administration of Study Drug

Each subject will receive a CB2679d loading dose of 50 IU/kg IV, followed 35 ± 5 minutes later with a SC dose of 100 IU/kg, and SC administration daily until Day 28 (total 1 IV dose and 28 SC doses).

This document is confidential.

Statistical Analysis Plan for Interventional Studies
Sponsor: Catalyst Biosciences, Inc.; Protocol No.: DLZ-201

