11.1. Extent of Exposure

Exposure to study drug (in days) will be calculated:

Exposure overall = number of days where study drug was administered.

Exposure will be summarized and listed. Details on study drug administration and drug accountability will be listed as well.

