11.2. Treatment Compliance

Study drug compliance (%) is calculated as ratio of the number of days study drug reported as administered and the number of days of administration expected. [in days]. Compliance will be summarized and listed.

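### Protocol version 2.0 states two regimens: Appendix B gives 70 IU/kg IV and 140 IU/kg SC, the body and the SAP give 50 and 100 IU/kg, a factor of 1.4 in every dose

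*Protocol*

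**What the plan says.** Section 6.1.2 of protocol version 2.0 gives a "CB2679d loading dose of 50 IU/kg IV, followed 35 ± 5 minutes later with a 100 IU/kg, with SC administration daily until Day 28". The same 50 and 100 IU/kg stand in Section 1.1 (treatment description and dosage paragraph), Section 1.3 footnote 7, Section 4.1 and Section 8.1.2.2. SAP Section 3.7 agrees: "CB2679d loading dose of 50 IU/kg IV, followed 35 ± 5 minutes later with a SC dose of 100 IU/kg". So do SAP Section 3.3 and the schedule footnote in SAP Section 3.8.

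Appendix B of the same protocol version says otherwise: "Day 1: Administer single IV 70 IU/kg loading dose of Dalcenonacog alfa", a 140 IU/kg SC dose 30 minutes later, and then "Day 2 to 28: Administer SC 140 IU/kg dose of Dalcenonacog alfa". The page carries the version 2.0 running header, the 28-day treatment block, screening genotyping and the Day 29 to 33 washout. It is current text, not the amendment log and not the superseded version 1.0.

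Appendix B and the body also differ on three points of schedule:

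- Appendix B has a Day 1 Hour 7 assessment. The Schedule of Activities and Section 4.1 have none.
- Appendix B places a platelet-only count at Day 1 Hour 7 and lists none on Day 2. Section 8.1.2.4 places the platelet-only count on Day 2 alone.
- Appendix B has no Day 3 visit. Section 4.1 requires a Day 3 pre-dose sample, and SAP Section 9.4 uses it.

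**The concern.** The primary objective is "To evaluate the dose required to achieve steady-state FIX levels >12% of a SC prophylaxis treatment regimen of CB2679d", and Protocol Section 9.1 promises to report that dose with a 95% confidence interval. A single regimen is given to six subjects, so the administered IU/kg is the figure that gives the result its meaning. One study team holds two versions of it in one document. Subjects self-administer from Day 2, so a wrong instruction could be repeated over 27 doses. A 1.4-fold difference in a coagulation factor also bears on subject safety.

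The planned exposure and compliance summaries would not show which regimen was used. SAP Section 11.1 defines "Exposure overall = number of days where study drug was administered", and Section 11.2 defines compliance as the "ratio of the number of days study drug reported as administered and the number of days of administration expected". Neither contains an amount of drug.

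**Working it through.** **Inputs.** Appendix B: 70 IU/kg IV, 140 IU/kg SC on Day 1 and on each of Days 2 to 28. Protocol body and SAP: 50 IU/kg IV, 100 IU/kg SC daily, 28 SC doses. The number of SC doses in Appendix B is 1 + 27 = 28, the same as in the body.

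| Quantity | Appendix B | Body and SAP | Ratio |
|---|---|---|---|
| IV load (IU/kg) | 70 | 50 | 1.4 |
| Each SC dose (IU/kg) | 140 | 100 | 1.4 |
| Day 1 total (IU/kg) | 70 + 140 = 210 | 50 + 100 = 150 | 1.4 |
| Cumulative (IU/kg) | 70 + 28 × 140 = 3,990 | 50 + 28 × 100 = 2,850 | 1.4 |
| Exposure (days) | 28 | 28 | 1.0 |
| Compliance | 28/28 = 100% | 28/28 = 100% | 1.0 |

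The cumulative difference is 3,990 − 2,850 = 1,140 IU/kg per subject.

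**Pre-dose FIX samples.** The body and SAP Section 9.4 name Days 2, 3, 7, 14, 21 and 28, which is six. Appendix B gives Days 2, 7, 14, 21 and 28, which is five. That count assumes its Day 2 draw, labelled as 24 hours after the SC dose, comes before the Day 2 injection; by label alone only four are pre-dose. Either count meets the SAP's minimum of three valid results, so the steady-state analysis would still run. The SAP's example contrast of Day 3 with Days 7, 14, 21 and 28 could not be estimated.

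**IV-to-SC interval.** Appendix B has 30 minutes. The body has 35 ± 5, that is 30 to 40 minutes. Footnote 7 reads "IV load dose (50 IU/kg) followed by SC dose (100 IU/kg) 30 minutes (+ 30 mins) after", that is 30 to 60 minutes. The three overlap at 30 minutes, so this is loose wording and not a contradiction of the same kind.

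**Does 1.4 matter near 12%? Illustration only.** Section 2.2.2 reports a median of 15.7% after six daily doses of 150 IU/kg, and a half-life of 63.2 hours. Assume dose proportionality and no IV load.

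- After six doses: 15.7 × 100/150 = 10.5% and 15.7 × 140/150 = 14.7%.
- Fraction of steady state reached after six daily doses: 1 − 2^(−144/63.2) = 0.794.
- At steady state: 10.5/0.794 ≈ 13.2% and, from the unrounded 14.65, 14.65/0.794 ≈ 18.5%.

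The two doses straddle 12% in the first case and both exceed it in the second. The protocol itself says the IV load raised levels more than additively, so these figures are not predictions and favour neither dose. They show only that a factor of 1.4 is not negligible at this threshold.

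**The case against.** The case for treating this lightly is that Appendix B is the only outlier. Every other dose statement in version 2.0 and in the SAP agrees, no section of the version 2.0 body sends the reader to Appendix B, Sections 8.1 to 8.1.3 point to the Schedule of Activities, and Section 6.2.3 says dosing details come from the sponsor. The primary endpoint is a count of subjects above 12%, and IU/kg is not an input to that count. The SAP also lists drug administration and accountability for every subject (Listings 16.2.5.1, 16.2.5.2 and 16.2.5.4) and says FIX summaries rest on the dose actually given, so with six subjects the truth could be recovered.

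Much of this stands. It lowers the likelihood that the Appendix B regimen was followed, and it means the listings could reveal the dose even though the summary tables could not. The lost Day 3 contrast is only an example in the SAP and adds little. The cumulative figures restate the ratio and enter no planned analysis.

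None of it removes the conflicting instruction. The dosing lines in Appendix B were themselves edited for version 2.0: the product name, the route abbreviation and the last dosing day all changed from version 1.0. A reader has no reason to take the page as out of date. The count of subjects above 12% needs no IU/kg, but the objective it serves does.

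**Conclusion.** The contradiction is real, lies in current text and must be corrected. The IV load, each SC dose and the cumulative amount all differ by a factor of 1.4 (3,990 against 2,850 IU/kg per subject, assuming all 28 SC doses are given). Day-based exposure and compliance are identical under the two regimens. The schedule differences (Day 1 Hour 7, platelet count, Day 3) are genuine but secondary, and the interval wording is minor. How likely misuse was cannot be settled from the documents, and the conclusion does not depend on it. Nothing here says which dose or schedule is correct.

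**What to change.** Reconcile Appendix B with Protocol Sections 1.1, 1.3 (footnote 7), 4.1, 6.1.2 and 8.1.2 and with SAP Sections 3.3, 3.7 and 3.8, so that one dose, one IV-to-SC interval and one sampling and platelet schedule appear throughout. Send the site a clarification.

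The documents do not say when dosing took place. The SAP is dated May 2019 and its note to file July 2020, so the records check may be the step that matters most. If dosing has occurred, confirm from the administration records which dose each subject received, and report the actual IU/kg beside the day-based summary in Table 14.1.5.1.

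The cost is an administrative amendment or clarification letter and, if dosing has occurred, a records check for six subjects and one added line in the exposure table.
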